Official title: Maximizing Use of Continuous Positive Airway Pressure in Stroke Rehabilitation Patients With Obstructive Sleep Apnea

NCT number: 02809430

Document date: March 10, 2019

Design: Single-arm, open-label study

Objectives: To assess the effectiveness of a multifaceted and intensive adherence program on 3month CPAP adherence and measures of stroke outcome (NIH stroke scale and Functional Independence Measure) among stroke patients undergoing inpatient rehabilitation (IPR)

Methods:

Eligible stroke patients (Table I) were enrolled and trialed auto-adjusting CPAP (4–20 cm H2 O; Dream Station, Philips Respironics) over a 3-night run-in period during IPR. Devices were interrogated for nightly usage, average pressure, and a residual apnea-hypopnea index (the respiratory events per hour of sleep). At the end of the run-in period, evidence of OSA was determined based on airflow resistance detected by the machine (see diagnosis of OSA below). Patients with evidence of OSA were eligible for CPAP treatment during IPR and after discharge from IPR. Nurses, respiratory therapists, sleep technologists, and clinical psychologists initiated the SCOUTS intensive CPAP adherence protocol during IPR emphasizing early CPAP tolerance, individual motivation (Table II) and support throughout the treatment period. The primary end point was CPAP adherence over 90 days from CPAP initiation, defined as \geq 4 hours of use on \geq 70% of days. Secondary efficacy end points were changes in the motor and cognitive components of the Functional Independence Measure (FIM) between admission and 3 to 4 months after discharge from IPR and in the National Institutes of Health Stroke Scale (NIHSS) between enrollment and 90 days.

Diagnosis of obstructive sleep apnea (OSA)

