recovery and met with a clinical psychologist for motivational interviewing (MI) during IPR to discuss patients' readiness to change, confidence in using CPAP and coping techniques to adjust to CPAP use (see Table II). The 30-minute face-to-face MI sessions occurred within one week of starting auto-adjusting CPAP. The MI session were focused on building motivation to use CPAP and alter the subject's decisional balance about using CPAP as it relates to patient-specific goals. To improve support, the adherence program included nightly visits by respiratory therapists during IPR to improve self-efficacy with CPAP and tailored written feedback prior to discharge from the IPR unit detailing CPAP download data, adjustments made during IPR and goals and barriers for CPAP use. Phone calls were also made weekly for one month after discharge from the IPR unit to encourage CPAP use and troubleshoot any device or mask problems.

Efficacy Measures

The National Institutes of Health Stroke scale (NIHSS; range, 0 to 42; higher scores indicate greater neurologic impairment) scores were obtained in-person on enrollment and at 90 ± 7 days from enrollment. The Functional Independence measure (FIM) scores were obtained as part of routine clinical care. The FIM included a motor and cognitive component (motor range, 13-91; cognitive range, 5 to 35; lower scores indicate greater functional disability). The admission FIM scores were obtained in-person by rehabilitation nurses and therapists upon admission to the IPR unit and follow-up FIM scores were obtained as part of routine clinical care through phone interview by IT Health Track, Inc., between 3 and 4 months from IPR unit discharge (mean 106 days); telephone response rates are approximately 60%.

Statistical Analyses

We compared baseline demographics, stroke severity and rehabilitation characteristics by adherence, using t-tests and Chi-squared tests as appropriate. To evaluate for predictors of adherence (Table III), we performed logistic regression, adjusting for baseline demographic covariates determined *a priori* including age (≥ 65 years), race/ethnicity (White versus non-White or Hispanic), sex, obesity (body mass index ≥ 30 kg/m²), baseline NIHSS score ≥ 5 and inpatient rehabilitation length of stay (weeks). As those with aphasia were noted to be adherent to CPAP, we added this stroke characteristic into separate models post-hoc.

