We examined for differences in baseline, 3-month and changes between baseline and 3- months in NIHSS, motor FIM and cognitive FIM by CPAP adherence using the t-test with unequal variances (Table IV). We also evaluated for association of CPAP adherence with 3-month NIHSS and cognitive FIM change using linear regression in models adjusting for age ≥ 65 years, sex, race/ethnicity, body mass index ≥ 30 , and baseline NIHSS score at study enrollment (Table IV). Finally, we evaluated the proportion of adherent and non-adherent participants who had improvement in the cognitive FIM and NIHSS, which was greater than the mean improvement among the entire sample: ≥ 7 for cognitive FIM improvement and ≥ 4 for NIHSS improvement (Table V).

Table I. Main Selection Criteria

Inclusion Criteria

Informed consent

Acute ischemic stroke or intraparenchymal hemorrhage

Age \geq 18 years

Admission to inpatient stroke rehabilitation unit at Harborview Medical Center and the University of Washington Medical Center

Exclusion Criteria

Stroke related to bleeding disorder, substance abuse, tumor, vascular malformation, trauma or other secondary cause

Active CPAP use at time of enrollment

Advanced congestive heart failure (New York Heart Association class 3 or 4)

Requiring supplemental oxygen or nasogastric feeding tube

Participation in another research outcome study

Table II. Motivational Interviewing Data Form

Subject's understanding of stroke and sleep apnea:

- Subject's readiness to change:
- □Pre-contemplation
- □Contemplation
- □Preparation
- \Box Action
- □Maintenance

Any small achievable subgoals:

 \Box YES \Box NO

Subject's reason for using CPAP:

□Stroke prevention

□Stroke recovery

□Sleep improvement

 $\Box Other$

Subject's reason for not using CPAP:

□Claustrophobia

□Anxiety

□Sleep disturbance

 \Box Mask fit or leak problems

□Device problems

 $\Box Other$

On a scale of 1-10, how important do you think it is for you to treat sleep apnea and use the

CPAP device?

On a scale of 1-10, how confident are you in your ability to use the CPAP device from now until the next time we meet?

Table III. Baseline factors associated with 3-month CPAP adherence, odds ratio (95% confidence interval)*

*All models included age, sex, obesity and weeks on inpatient rehabilitation. Model 1 additionally included race and baseline NIHSS \geq 5; model 2 for race and aphasia; model 3 for race, aphasia and baseline NIHSS \geq 5.

	Model 1	Model 2	Model 3

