White race	10.9 (1.7, 701)	3.7 (0.7, 19.8)	8.2 (1.1, 62.3)
Aphasia		12.9 (1.3, 129)	8.0 (0.7, 87.7)
NIHSS≥5	14.9 (1.9, 115.7)		10.6 (1.2, 92.6)

	Adherent, mean (SD)		Non-adherent, mean (SD)			P-value*		
	Baseline	3-months	Change	Baseline	3-months	Change	Unadjusted	Adjusted
Motor FIM†	48.5 (11.2)	79.7 (12.1)	31.2 (15.7)	47.3 (17.6)	77.5 (10.8)	30.2 (13.2)	0.83	0.65
Cognitive FIM†	24.1 (6.9)	32.4 (3.7)	8.2 (6.5)	28.5 (3.9)	33.1 (2.4)	4.6 (3.0)	0.03	0.02
NIHSS ‡	6.5 (4.3)	2.7 (3.1)	-3.8 (2.6)	4.1 (2.2)	2.6 (2.6)	-1.6 (2.2)	0.003	0.03

Table IV. Improvement in cognitive FIM and NIHSS associated with CPAP adherence

CPAP indicates continuous positive airway pressure; SD, standard deviation; NIHSS, National Institutes of Health Stroke Scale; Cognitive FIM, cognitive component of Functional Independence measure

* Difference between mean changes in outcome between adherent and non-adherent patients: unadjusted using t-test with unequal variances and adjusted for age, sex, body mass index, race and baseline NIHSS using linear regression

† n=22 adherent group and n=12 non-adherent

‡ n=30 adherent group and n=19 non-adherent

Table V. Improvement in cognitive FIM and NIHSS associated with CPAP adherence

Patient characteristics	Adherent	Non-adherent	P -value
Cognitive FIM improvement ≥ 7, n (%)*	10 (45)	3 (25)	0.24
NIHSS improvement \geq 4, n (%) [†]	16 (53)	3 (16)	0.01

* n=22 adherent group and n=12 non-adherent

† n=30 adherent group and n=19 non-adherent

REFERENCES

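### Ischemic stroke and intraparenchymal hemorrhage are pooled and stroke type is in no Table IV outcome model, so a different mix of types in the self-selected adherence groups could contribute to the NIHSS and FIM differences

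*Combined protocol and SAP*

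**What the plan says.** The combined protocol and SAP describes a "Single-arm, open-label study". Table I admits "Acute ischemic stroke or intraparenchymal hemorrhage", with no cap, stratum or planned split by type.

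Under Statistical Analyses, patients are grouped by observed CPAP adherence and compared on NIHSS and FIM change, first by unequal-variance t-tests and then by linear regression. The regressions are described as "models adjusting for age ≥ 65 years, sex, race/ethnicity, body mass index ≥ 30 , and baseline NIHSS score at study enrollment". The footnote to Table IV gives the same set: "adjusted for age, sex, body mass index, race and baseline NIHSS using linear regression". The Table V proportions are unadjusted.

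The description of baseline comparisons reads "We compared baseline demographics, stroke severity and rehabilitation characteristics by adherence" and does not name stroke type. One further stroke characteristic was considered: "As those with aphasia were noted to be adherent to CPAP, we added this stroke characteristic into separate models post-hoc". Those are the Table III models for predictors of adherence, not the outcome models. Stroke type is in neither set, and no count by type is given.

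**The concern.** Adherence is a behaviour seen after enrolment, so the two groups in Table IV are not comparable by design. Covariate choice is the only protection against confounding. Stroke type is fixed at baseline and should be known for every participant, because it is part of eligibility.

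If recovery differs between the types at the same starting deficit, and the share of hemorrhage differs between adherers and non-adherers, part of the difference in NIHSS or FIM change belongs to type and not to CPAP use. Baseline NIHSS measures how large the deficit is. It does not measure how a given type recovers from a deficit of that size.

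At stake is the reading of the secondary outcomes. The stated objective is effectiveness on stroke outcome measures, and Table IV is where a reader will look for it. The primary endpoint, CPAP adherence itself, is not affected.

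**Working it through.** **Inputs.** Table IV gives NIHSS for "n=30 adherent group and n=19 non-adherent". Adherent mean (SD): baseline 6.5 (4.3), 3 months 2.7 (3.1), change -3.8 (2.6). Non-adherent: 4.1 (2.2), 2.6 (2.6), -1.6 (2.2). FIM has 22 and 12 patients. Counts and outcomes by stroke type are not given.

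**1. The plan's own figure.** Unadjusted NIHSS difference in change: -3.8 - (-1.6) = -2.2. SE = √(2.6²/30 + 2.2²/19) = 0.69. Welch p = 0.0028, against the stated 0.003. Reproduced.

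**2. Size of a possible bias (both factors assumed).** Bias = (gap in share of one type between groups) × (difference in mean change between types at equal baseline).
- 0.10 × 1 = 0.1 NIHSS point.
- 0.20 × 2 = 0.4 NIHSS point.

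The sign can go either way.

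**3. Could such a gap arise?** With an assumed hemorrhage share q, the chance SD of the gap is √[q(1-q)(1/n₁ + 1/n₂)].
- NIHSS sample (30 and 19): q = 0.10 gives 0.088, so a 95% range of ±17 points. q = 0.30 gives 0.134, so ±26 points.
- FIM sample (22 and 12): ±21 and ±32 points.

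A gap of 10 to 20 points would be unremarkable at these sizes. This does not show that one occurred.

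**4. Can a tipping point be stated?** The adjusted NIHSS coefficient is not reported, only p=0.03. A comparison adjusted for baseline NIHSS alone can be rebuilt from the SDs.
- Covariance of baseline and 3-month score = (SD₀² + SD₃² - SD_change²)/2, which is 10.67 (adherent) and 3.38 (non-adherent).
- Covariance of change with baseline = that value minus SD₀²: 10.67 - 18.49 = -7.82, and 3.38 - 4.84 = -1.46.
- Pooled slope = (29 × -7.82 + 18 × -1.46)/(29 × 18.49 + 18 × 4.84) = -253.06/623.33 = -0.406.
- Residual sum of squares = 29 × 6.76 + 18 × 4.84 - 253.06²/623.33 = 180.4 on 46 df. Mean square 3.92.
- SE = √[3.92 × (1/30 + 1/19 + 2.4²/623.33)] = 0.61.

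| Means used | Crude difference | Adjusted difference: crude + 0.406 × 2.4 | 95% CI | p |
|---|---|---|---|---|
| Printed change means | -2.2 | -1.23 | -2.46 to +0.004 | 0.051 |
| 3-month minus baseline means | (2.7 - 6.5) - (2.6 - 4.1) = -2.3 | -1.33 | -2.56 to -0.10 | 0.035 |

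The two rows differ by 0.10 point only because Table IV is rounded to one decimal. The result lies on either side of 0.05 depending on which printed means are used. No tipping point in NIHSS points can be read from it.

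**5. Cost of a type term.** The present models have an intercept, adherence and five covariates, so 7 parameters; type makes 8. Residual df: 49 - 8 = 41 for NIHSS and 34 - 8 = 26 for FIM. At an assumed hemorrhage share of 10 to 30%, the non-adherent FIM group would hold about 12 × 0.10 = 1.2 to 12 × 0.30 = 3.6 such patients.

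**The case against.** The strongest reply is that a confounder must be related to both adherence and recovery, and the documents show neither link for stroke type. Both factors in the bias product are assumed, the direction is unknown, and adding type could as easily strengthen the result as weaken it. Pooling two types in a small rehabilitation study is not itself an error. This stands, and it limits the point to a gap in protection and reporting.

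Stroke type is also not the best-evidenced candidate. The documents themselves link aphasia to adherence (Table III, model 2 odds ratio 12.9, 95% CI 1.3 to 129), and aphasia too is absent from the outcome models. Baseline imbalance is visible in Table IV: NIHSS 6.5 against 4.1, cognitive FIM 24.1 against 28.5. The rebuild in step 4, applied to cognitive FIM with its own baseline and the printed change means, leaves a difference of 0.2 point (p=0.86). For that outcome the baseline score matters more visibly than stroke type. This stands as a matter of priority. It does not remove the gap.

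It may be said that baseline NIHSS already covers type. It does so only for differences that act through starting severity.

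It may also be said that the analysis text speaks of association only. That is so, but the objective speaks of effectiveness, so the outcome comparison will carry more weight than the word suggests.

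**Conclusion.** The point holds as a minor one. Two stroke types are pooled, type is in none of the Table IV models, and self-selected adherence groups give no protection against a different mix. Such a mix could contribute to the NIHSS and FIM differences. The size and direction of any bias are unknown; 0.1 to 0.4 NIHSS point is an illustration that rests on assumed shares and assumed differences in recovery.

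A reader might infer two stronger things, and the documents support neither.
- **That stroke type did confound Table IV.** There are no data by type from which to judge this.
- **That a bias of 0.10 NIHSS point would carry the adjusted result past 0.05.** That margin lies within the rounding of Table IV (rebuilt p=0.035 or 0.051). The rebuild also adjusts for baseline NIHSS alone, and the coefficient of the study's five-covariate model cannot be recovered.

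**What to change.** - Report the number of ischemic and hemorrhagic strokes by adherence group beside Table IV, for the NIHSS sample (30 and 19) and the FIM sample (22 and 12). The counts alone would show whether the mix differed.
- Add stroke type (hemorrhage yes/no) to the regressions for NIHSS, cognitive FIM and motor FIM. Label this an exploratory sensitivity model, since results are already tabulated, and show it next to the existing adjusted results.
- If the adherence association changes materially, limit the conclusion on stroke outcome accordingly.

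The cost is one residual degree of freedom per model and no new data collection, provided type was recorded at eligibility. If few hemorrhage patients fall in the non-adherent FIM group (n=12), the type term there will be imprecise, and little change in the adherence estimate should not be taken as proof that type does not matter.

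### The Table IV outcome models omit time since stroke, so a timing difference between adherence groups could bias the NIHSS and FIM comparisons in either direction, and the adjusted NIHSS result is fragile to it

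*Combined protocol and SAP*

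**What the plan says.** **Timing of assessments (Efficacy Measures).** NIHSS "scores were obtained in-person on enrollment and at 90 ± 7 days from enrollment". For FIM, "The admission FIM scores were obtained in-person by rehabilitation nurses and therapists upon admission to the IPR unit"; follow-up was by telephone 3 to 4 months after discharge from the unit. Neither schedule is counted from the stroke.

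**Eligibility (Table I).** The relevant criterion is "Acute ischemic stroke or intraparenchymal hemorrhage", together with admission to one of two inpatient rehabilitation units. No minimum or maximum number of days from onset is given.

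**Outcome models.** Statistical Analyses describes "models adjusting for age ≥ 65 years, sex, race/ethnicity, body mass index ≥ 30 , and baseline NIHSS score at study enrollment". The Table IV footnote gives the same five covariates: "adjusted for age, sex, body mass index, race and baseline NIHSS using linear regression". The unadjusted tests and the Table V proportions have no covariates. The only time variable in any model is rehabilitation length of stay in weeks, which is used in the models for predictors of adherence (Table III) and not in the outcome models.

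**Sample.** For NIHSS, "n=30 adherent group and n=19 non-adherent". For FIM, 22 and 12.

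**The concern.** If recovery after stroke slows with time, two patients with the same NIHSS at enrollment do not have the same improvement ahead of them when one is scored at one week and the other at four. Adjusting for the baseline score fixes where the patient is on the scale, but not where the patient is on the recovery curve.

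This matters because the comparison is not randomised. Adherence is observed within a single arm, and nothing in the design balances time since stroke between the groups. If adherers were enrolled earlier, part of their larger improvement would be timing. If they were enrolled later, the association would be understated.

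The tabled means do not settle the matter. On NIHSS the groups start apart (6.5 and 4.1) and finish together (2.7 and 2.6). Cognitive FIM does the same (24.1 and 28.5, then 32.4 and 33.1). That pattern fits a CPAP effect, but also different positions on the recovery curve or regression to the mean. What is at stake is the reading of the secondary outcomes, for which the stated objective speaks of effectiveness. The primary endpoint, adherence itself, is untouched.

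**Working it through.** **1. Reproduce the plan's unadjusted figures.** Inputs are the Table IV means, SDs and group sizes. Welch's test for NIHSS change:
- difference = 3.8 − 1.6 = 2.2 points
- SE = √(2.6²/30 + 2.2²/19) = √(0.225 + 0.255) = 0.693
- t = 2.2/0.693 = 3.175 on 43.0 df, p = 0.0028 (stated 0.003)
- 95% CI 0.80 to 3.60

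The same calculation gives p = 0.035 for cognitive FIM (stated 0.03) and 0.845 for motor FIM (stated 0.83). All are close to the stated values, given rounded inputs.

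**2. Approximate the adjusted NIHSS result.** Table IV gives an adjusted P-value (0.03) but no adjusted estimate. An analysis of covariance of 3-month NIHSS on group and baseline NIHSS can be rebuilt from the table. With baseline as a covariate, modelling the 3-month score or the change gives the same group coefficient.
- Within-group covariance = (SD_base² + SD_3m² − SD_change²)/2. Adherent: (4.3² + 3.1² − 2.6²)/2 = 10.67. Non-adherent: (2.2² + 2.6² − 2.2²)/2 = 3.38.
- Sxx = 29×4.3² + 18×2.2² = 623.3
- Sxy = 29×10.67 + 18×3.38 = 370.3
- Syy = 29×3.1² + 18×2.6² = 400.4
- Slope B = 370.3/623.3 = 0.594
- Adjusted difference = (2.7 − 2.6) − 0.594×(6.5 − 4.1) = −1.33, that is, 1.33 points in favour of adherers
- Residual variance = (400.4 − 0.594×370.3)/46 = 3.92
- SE = √[3.92×(1/30 + 1/19 + 2.4²/623.3)] = 0.611
- t = 2.17 on 46 df, p = 0.035
- 95% CI 0.10 to 2.56

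This omits age, sex, race and BMI, but its p is close to the stated 0.03. A bias of 0.10 points would bring the lower limit to zero.

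**3. What a week could be worth (assumed model).** The documents give no recovery curve. Assume the deficit is a permanent part plus a recoverable part that decays exponentially. A fraction r = 0.5-0.7 is recoverable at onset, the time constant is τ = 20-45 days, and baseline is taken at t = 7-28 days.
- Mean baseline NIHSS = (30×6.5 + 19×4.1)/49 = 5.57
- Expected 90-day improvement = 5.57 × R/(1 − r + R) × (1 − e^(−90/τ)), with R = r·e^(−t/τ)
- Average loss per week of later baseline, days 7 to 28: smallest at r = 0.7, τ = 45, (3.21 − 2.68)/3 = 0.18; largest at r = 0.7, τ = 20, (3.43 − 2.01)/3 = 0.47

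The observed baseline score is held fixed here, so this is the part that adjusting for baseline NIHSS leaves behind.

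**4. Effect on the rebuilt result.** Take a one-week mean imbalance with SE held at 0.611 on 46 df:

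| Imbalance | Difference | t | p |
|---|---|---|---|
| Adherers earlier, 0.18 | 1.33 − 0.18 = 1.15 | 1.87 | 0.07 |
| Adherers earlier, 0.47 | 1.33 − 0.47 = 0.86 | 1.40 | 0.17 |
| Adherers later, 0.18 | 1.33 + 0.18 = 1.51 | 2.46 | 0.018 |
| Adherers later, 0.47 | 1.33 + 0.47 = 1.80 | 2.94 | 0.005 |

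As shares of the rebuilt difference, 0.18/1.33 = 14% and 0.47/1.33 = 35%. Against the raw 2.2 points they are 8% and 21%. No corresponding figure is offered for FIM.

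**The case against.** **Confounding is not shown.** This is the strongest reply, and it stands. Bias needs time since stroke to differ by adherence, and the documents give no timing for either group. Adherers had the more severe strokes on NIHSS. If that meant they reached rehabilitation later, the omission would understate the association. The recovery fraction, time constant and one-week imbalance are all assumptions.

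**The absence of a window may be less stark than it looks.** Table I lists main criteria and may be abridged. Acute stroke with admission to inpatient rehabilitation narrows the spread, and rehabilitation characteristics were compared by adherence without being itemised. That is fair, but no limit is stated, and timing is not named among the variables compared.

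**The models are small and secondary.** The FIM models already carry adherence and five covariates for 34 patients, and the text calls these results associations. This supports adding a single term and no more. It does not remove the need to look at timing.

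**Stronger readings that do not hold.** A reader might infer that:
- *Natural recovery explains the adherence result.* The documents cannot show this without timing by group.
- *Motor FIM gains of 31.2 and 30.2 points measure natural recovery.* They also contain inpatient therapy and a change from in-person to telephone scoring.
- *Leaving out time since stroke costs much precision.* With an assumed one-week SD in timing and a change SD near 2.4, the share of variance is (0.18/2.4)² to (0.47/2.4)², about 0.5-4%. That is a weak argument, and the point does not rest on it.

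**Conclusion.** The concern holds as a possible bias of unknown size and direction. The documents establish three things: the baselines are not anchored to the stroke, no onset window is stated, and the outcome models omit time since stroke although the groups are self-selected. They do not establish that timing differed between the groups.

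The point deserves action because the adjusted NIHSS finding has so little margin. One week in the unfavourable direction is enough to lift p above an assumed two-sided 5% level across the whole assumed range, and one week the other way would firm the result up. This rests on the exponential recovery model, on a reconstruction that uses baseline NIHSS as its only covariate, and on an unchanged standard error. For cognitive and motor FIM the same omission exists, but its size has not been estimated.

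**What to change.** Report days from stroke onset to baseline by adherence group, beside the other baseline characteristics: to enrollment for NIHSS and to rehabilitation admission for FIM. Add the same quantity, on the log scale, as one continuous term in each Table IV linear model. Show the result next to the existing adjusted one, not in place of it, with the estimate and confidence interval as well as the P-value. If timing proves similar in the two groups, this source of doubt is largely removed. If it does not, readers can see how much of the association remains.

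The cost is retrieving onset dates, which should be in the admission record, and one degree of freedom in models of 34 to 49 patients. The sponsor should also accept that the P-value may become less favourable.

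### The Table IV outcome models leave out aphasia, which the study found associated with adherence, so residual confounding of the secondary cognitive FIM and NIHSS associations cannot be excluded

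*Combined protocol and SAP*

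**What the plan says.** The design is single-arm and open-label. The primary endpoint is CPAP adherence over 90 days; changes in FIM and NIHSS are secondary.

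Aphasia appears in one part of the analysis only. For the models that predict adherence, Statistical Analyses states: "As those with aphasia were noted to be adherent to CPAP, we added this stroke characteristic into separate models post-hoc". The Table III footnote places it in Model 2, which has no NIHSS term, and in Model 3 ("model 3 for race, aphasia and baseline NIHSS" dichotomised at 5).

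The outcome models reverse the roles, with adherence as the exposure. Statistical Analyses lists their covariates as age ≥ 65, then "sex, race/ethnicity, body mass index ≥ 30 , and baseline NIHSS score at study enrollment (Table IV"). The Table IV footnote agrees: "adjusted for age, sex, body mass index, race and baseline NIHSS using linear regression". Neither mentions aphasia, and no reason is given for leaving it out.

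**The concern.** Patients chose, or were able, to adhere; nobody was randomised to it. A baseline factor tied to adherence confounds the adherence-outcome contrast if it also predicts recovery given the other covariates. The study noticed one such candidate and modelled it where adherence was the outcome, but did not carry it into the models where adherence is the exposure.

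Aphasia could plausibly bear on both outcomes, since it is a stroke deficit. If patients with aphasia improved more, part of their gain would be credited to adherence. If they improved less, the association would be understated. At stake is whether the adjusted P-values of 0.02 (cognitive FIM) and 0.03 (NIHSS) can be read as evidence that adherence goes with better recovery.

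**Working it through.** **1. Reproduce the unadjusted P-values in Table IV.** Inputs are the change means, SDs and group sizes (for FIM, "n=22 adherent group and n=12 non-adherent"; for NIHSS, 30 and 19). Welch: SE = √(s₁²/n₁ + s₂²/n₂), t = difference/SE.

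- Cognitive FIM: difference 8.2 − 4.6 = 3.6; SE = √(6.5²/22 + 3.0²/12) = 1.634; t = 2.20 on 31.4 df; P = 0.035 (0.029 to 0.042 allowing for rounding of the inputs; stated 0.03); 95% CI 0.27 to 6.93.
- NIHSS: difference −3.8 − (−1.6) = −2.2; SE = √(2.6²/30 + 2.2²/19) = 0.693; t = −3.18 on 43.0 df; P = 0.0028 (0.0015 to 0.0049; stated 0.003); 95% CI −3.60 to −0.80.
- Motor FIM: P = 0.845 (0.829 to 0.861; stated 0.83).

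All three agree with the table within rounding.

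**2. How firmly is aphasia tied to adherence?** From the Table III intervals, SE(log OR) = (ln upper − ln lower)/(2 × 1.96).

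- Model 2: (ln 129 − ln 1.3)/3.92 = 1.173; z = ln 12.9/1.173 = 2.18; P about 0.03.
- Model 3: (ln 87.7 − ln 0.7)/3.92 = 1.232; z = ln 8.0/1.232 = 1.69; P about 0.09.

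The estimate falls but stays large once NIHSS≥5 is included. Both intervals are very wide.

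**3. How much margin do the adjusted results have?** Adjusted coefficients are not reported, so work back from P. Assume complete cases, one term per covariate and two-sided tests, so df = n − 7 (intercept, adherence, five covariates). With the SE held, P reaches 0.05 when the coefficient shrinks by 1 − t(0.975)/t(observed).

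- Cognitive FIM: n = 34, df = 27; P = 0.02 gives t = 2.473; 1 − 2.052/2.473 = 17% (14% to 21% allowing for rounding of P).
- NIHSS: n = 49, df = 42; P = 0.03 gives t = 2.246; 1 − 2.018/2.246 = 10% (7% to 13%).

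**4. How large an aphasia effect would matter?** The documents give no aphasia counts. Assume prevalence p₀ of 5% to 30% in non-adherent patients, and treat the reported odds ratios as if they were crude, so p₁ = OR·p₀/(1 − p₀ + OR·p₀). The gap p₁ − p₀ then runs from 0.246 (OR 8.0, p₀ = 5%) to 0.563 (OR 12.9, p₀ = 20%). Bias in the crude difference is roughly the aphasia effect on change times this gap.

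| | Cognitive FIM | NIHSS |
|---|---|---|
| Effect that removes the whole crude difference | 3.6/0.563 to 3.6/0.246 = 6.4 to 14.6 points | 2.2/0.563 to 2.2/0.246 = 3.9 to 8.9 points |
| Effect that brings the crude 95% CI to zero | 0.27/0.563 to 0.27/0.246 = 0.5 to 1.1 points | 0.80/0.563 to 0.80/0.246 = 1.4 to 3.3 points |

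These figures concern the crude differences and suppose that patients with aphasia improve more. The opposite sign would move the estimates away from zero.

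**The case against.** The strongest objection is that confounding needs two links and the documents show one. Nothing relates aphasia to change in cognitive FIM or NIHSS, so a reader who infers that the associations are confounded by aphasia, or are inflated by it, goes beyond the text. That stands.

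Nor does Table III settle that baseline NIHSS fails to capture aphasia. The Model 3 interval includes 1, and Model 3 uses NIHSS≥5, whereas the outcome models appear to use the score itself: Statistical Analyses gives cut-offs for age and body mass index there but none for NIHSS. Finer adjustment may absorb more of the aphasia signal. This also stands, but it does not close the question. An interval that crosses 1 does not rule out an imbalance in this sample, and the documents do not show that the score removes it.

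A reader might also take this as a threat to the trial's main result. It is not: FIM and NIHSS change are secondary. Motor FIM shows no association either way (0.83 and 0.65) and needs no extra model for this purpose.

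Finally, baseline cognitive FIM is a better-documented imbalance: 24.1 against 28.5 at baseline, 32.4 against 33.1 at three months, on a scale that ends at 35, and it is not a listed covariate. That is a separate gap. Adding aphasia would not directly repair it, and it does not answer the present point.

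**Conclusion.** The point holds as a limited one. Aphasia is missing from the outcome models, the study itself associated it with adherence, and adherence is not randomised. Residual confounding by aphasia therefore cannot be excluded; neither its presence nor its direction is shown.

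The sensitivity analysis matters because significance is fragile: a shrinkage of about 17% for cognitive FIM or 10% for NIHSS is enough to bring P to 0.05, given df = n − 7 and an unchanged SE. That the associations are wholly due to aphasia is not supported. Under the assumed prevalences, aphasia alone would have to shift cognitive FIM gain by at least 6.4 points, or NIHSS improvement by at least 3.9, to erase the crude differences.

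**What to change.** Beside the current Table IV models for cognitive FIM and NIHSS change, report a sensitivity model that adds aphasia (yes/no). Label it post hoc. For both versions give the adherence coefficient and its 95% CI, not only P, and give the number of patients with aphasia in each adherence group for each outcome. If the estimate shrinks materially, describe the association as not robust to aphasia. The current model need not be withdrawn, and the new one should not act as a veto on it.

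Aphasia is already recorded and modelled, so no new data are needed. The cost is one degree of freedom at n = 34 and n = 49, and possibly poor overlap. If aphasia prevalence in non-adherent patients were 5% to 10% (assumed), 12 such patients would include 0.6 to 1.2 with aphasia, and the chance of none is 0.95¹² = 54% to 0.90¹² = 28%. For the 19 in the NIHSS analysis it is 0.95¹⁹ = 38% to 0.90¹⁹ = 14%. At 30% prevalence the problem all but disappears (0.70¹² = 1%). With no non-adherent patient with aphasia, the aphasia coefficient comes from adherent patients alone and the adjusted estimate relies on additivity. The counts will show whether that is so, and the result should then be read with caution.
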